## 9.4. Statistical Analyses

The SAP will be developed and finalized for each sub-study before any analyses are performed and will describe the analyses and procedures for accounting for missing, unused, and spurious data. This section is a summary of the planned statistical analyses of the primary and secondary endpoints.

### 9.4.1. General Considerations

Each sub-study will be reported separately and by Phase 1b and Phase 2.

### 9.4.2. Primary Endpoint(s)

#### Phase 1b

DLT during the DLT-observation period is the primary safety endpoint of the Phase 1b for the combination evaluated. Analyses of DLT are based on the DLT-evaluable analysis set.

#### Phase 2

Refer to sub-study appendices for primary efficacy endpoints.

### 9.4.3. Secondary Endpoints

#### 9.4.3.1. Efficacy Analysis

Refer to sub-study appendices for secondary efficacy analyses.

#### 9.4.3.2. Safety Analyses

All safety analyses will be performed on the safety population.

Simple summary statistics (descriptive) will be presented for participants with SAEs, AEs of special interest, laboratory abnormalities, and other secondary safety endpoints during the on-treatment period (defined as the time from the first dose of study treatment through minimum of 30 days after last dose of study treatment or the start day of new anti-cancer drug – 1 day) unless otherwise specified in the SAP.

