#### **8.3.1. Time Period and Frequency for Collecting AE and SAE Information**

The time period for actively eliciting and collecting AEs and SAEs (“active collection period”) for each participant begins from the time the participant provides informed consent, which is obtained before the participant’s participation in the study (ie, before undergoing any study related procedure and/or receiving study intervention), through and including a minimum of 90 calendar days after the last administration of the study intervention.

During the long-term follow-up period in this study for survival, only SAEs will be actively elicited and collected after completion of the active collection period described above. The SAEs identified during long-term follow-up will be reported to Pfizer Safety on the CT SAE Report Form only if considered reasonably related to the study intervention.

For participants who are screen failures, the active collection period ends when screen failure status is determined.

If the participant withdraws from the study treatment and also withdraws consent for the collection of future information, the active collection period ends when consent is withdrawn.

Follow-up by the investigator continues throughout and after the active collection period and until the AE or SAE or its sequelae resolve or stabilize at a level acceptable to the investigator and Pfizer concurs with that assessment.

If a participant definitively discontinues or temporarily discontinues study intervention because of an AE or SAE, the AE or SAE must be recorded on the CRF and the SAE reported using the CT SAE Report Form.

Investigators are not obligated to actively seek AEs or SAEs after the participant has concluded study participation. However, if the investigator learns of any SAE, including a death, at any time after a participant has completed the study, and he/she considers the event to be reasonably related to the study intervention, the investigator must promptly report the SAE to Pfizer using the CT SAE Report Form.

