#### **8.3.1.2. Recording Nonserious AEs and SAEs on the CRF**

All nonserious AEs and SAEs occurring in a participant during the active collection period, which begins after obtaining informed consent as described in [Section 8.3.1](#), will be recorded on the AE section of the CRF.

The investigator is to record on the CRF all directly observed and all spontaneously reported AEs and SAEs reported by the participant.

If a participant begins a new anticancer therapy, the recording period for nonserious AEs ends at the time the new treatment is started; however, SAEs must continue to be recorded on the CRF during the above-indicated active collection period. Note that a switch to a commercially available version of the study intervention is considered as a new anticancer therapy for the purposes of SAE reporting.

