### **8.3.8. Adverse Events of Special Interest**

Any AE that is suspected to be a potential irAE is considered an AE of special interest (AESI). Specific guidance for the management of irAEs is provided in [Section 10.10](#).

All AESIs must be reported as an AE or SAE following the procedures described in [Sections 8.3.1](#) through [8.3.4](#). An AESI is to be recorded as an AE or SAE on the CRF. In addition, an AESI that is also an SAE must be reported using the CT SAE Report Form.

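### The default safety summaries end 30 days after last dose or at new anti-cancer therapy, while SAEs and immune-related AEs are collected to at least 90 days, so some collected events are left out of the reported rates

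*Protocol*

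**What the plan says.** **Reporting window.** Section 9.4.3.2 plans descriptive statistics for "participants with SAEs, AEs of special interest, laboratory abnormalities, and other secondary safety endpoints during the on-treatment period". The window itself is "the time from the first dose of study treatment through minimum of 30 days after last dose of study treatment". A second possible end is tied to subsequent treatment: "or the start day of new anti-cancer drug", less one day. The sentence closes with "unless otherwise specified in the SAP", so this is a default that the SAP may replace.

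**Collection window.** Section 8.3.1 starts active collection of AEs and SAEs at informed consent and runs it "through and including a minimum of 90 calendar days after the last administration of the study intervention". During survival follow-up, "only SAEs will be actively elicited and collected after completion of the active collection period described above". Section 8.2.8 schedules contacts at 30, 60, 90 and 180 days.

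**After new anticancer therapy.** Under section 8.3.1.2, recording of nonserious AEs stops when the new therapy starts, but "SAEs must continue to be recorded on the CRF during the above-indicated active collection period".

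**Immune-related AEs.** Section 8.3.8 makes any suspected immune-related AE (irAE) an AESI and has it recorded through the ordinary AE and SAE procedures, so the same collection period applies.

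**Sub-studies.** Sections 12.9.1.5.2.2 (Sub-Study A) and 13.9.1.5.2.2 (Sub-Study B) refer back to 9.4.3.2 for secondary safety analyses. Neither sets a longer window.

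**The concern.** The plan collects late SAEs and irAEs for a reason. Section 2.3 names immune-related AEs as important risks of sasanlimab. Section 13.2.3 expects overlapping irAEs when a second checkpoint inhibitor is added in Sub-Study B and says that the triplet's safety profile is not yet characterised. Safety and tolerability is a secondary objective of both Phase 2 parts (Tables 6 and 24).

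The summary rates are what most readers of the results will use, and by default they leave out part of what was collected. The cohorts are uncontrolled and small, so each omitted participant is visible in a rate.

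**Working it through.** No sample size, power or alpha is involved. The check sets the two windows side by side by day after last dose of study treatment.

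**Inputs**
- Default end of the summary window: day 30, or the day before new anti-cancer drug (9.4.3.2), read as the earlier.
- End of active collection: at least day 90 (8.3.1).
- SAEs after new therapy: still recorded within active collection (8.3.1.2).
- Nonserious AEs after new therapy: not recorded (8.3.1.2).

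**Case 1: no new therapy by day 90.**
Collected: days 1-90. Summarised: days 1-30. Not summarised: 90 − 30 = 60 days, and 60 / 90 = 67% of the post-dose collection period. This applies to SAEs and to nonserious irAEs.

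**Case 2: new therapy starts early.**
Take day 14 after last dose as an assumed date. The summary window ends on day 13. SAEs on days 14-90 are recorded but not summarised: 90 − 14 + 1 = 77 days. For nonserious irAEs there is no gap, because recording stops when the new therapy starts.

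**Case 3: new therapy starts between days 31 and 90.**
The summary window still ends on day 30. SAEs on days 31-90 are recorded but not summarised. For nonserious irAEs the gap runs from day 31 to the start of the new therapy.

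| Event type | No new therapy by day 90 | After new therapy starts |
|---|---|---|
| SAE, including serious irAE | Days 31-90 collected, not summarised | Collected to at least day 90, not summarised |
| Nonserious irAE | Days 31-90 collected, not summarised | Not collected, so nothing is omitted |

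**What one omitted participant does to a rate.**
- Sub-Study A Phase 2, about 62 participants: 1 / 62 = 1.6 percentage points.
- Each Sub-Study B Phase 2 arm, 20 participants: 1 / 20 = 5 percentage points.

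How many participants would be omitted does not follow from the protocol. It gives no rate of late-onset SAEs or irAEs and no distribution of time to new therapy.

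**The wording.** Section 8.3.1 uses *minimum of* to mean at least. In section 9.4.3.2 the same words are followed by *or* and a second date, which points to the earlier of two dates. If *at least 30 days* were meant, the window would have no defined end. The sentence needs correcting on either reading.

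**The case against.** **The SAP clause.** The sentence lets the SAP set another window, sections 9 and 9.4 allow the SAP to modify and detail the analyses, and the SAP is not available here. It therefore cannot be said that late events will be missing from the final tables. This stands and limits the point to the default. The protocol nevertheless states a specific default, and that default is shorter than its own collection period.

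**Two windows for two purposes.** Collection and on-treatment reporting can properly differ, and stopping at new therapy limits misattribution. This also stands: a reader might infer a contradiction, and there is none. It is a reason to keep the on-treatment table. It does not explain why no summary uses the remaining days.

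**Late events stay visible.** Section 9.4.3.2.1 plans AE listings and a listing of deaths with no window of their own. Section 8.3.1.1 requires SAEs in the active period to be reported within 24 hours irrespective of new therapy, and section 9.6 provides internal review of individual and summary data. A reader might infer that late events vanish from the report; the documents do not support that. Listings, however, do not give rates.

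**Weak supporting facts.** A reader might argue that monthly antibody dosing and six months of contraception show that 30 days is too short. The 28-day cycle belongs to Sub-Study A only; Sub-Study B runs on 21-day cycles. Contraception is required because of developmental toxicity (12.10.2, 13.10.2) and says nothing about irAE onset. The 30-day clock also starts at the last dose of study treatment, so a participant who stops sasanlimab but continues an oral partner drug stays in the window longer. None of this closes the gap on days 31-90 after the last dose of everything.

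**Importance.** Section 2 calls the study primarily exploratory, Phase 1b decisions rest on Cycle 1 DLTs, and the Phase 2 primary endpoints are response endpoints. No decision rule uses these safety rates. This stands and keeps the severity low.

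**Conclusion.** The point holds for the protocol's default. If section 9.4.3.2 is followed as written and read as the earlier date, two groups of collected events fall outside the SAE and AESI summary rates:
- SAEs with onset on days 31-90 or after new anticancer therapy;
- nonserious irAEs on days 31-90 in participants without new therapy.

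The size in time is 60 of at least 90 post-dose collection days. The size in participants is unknown. A reader might put a number on it by assuming that 5-10% have a first such event on days 31-90, which would give about 3-6 of 62 in Sub-Study A and 3-6 of 60 in Sub-Study B; nothing in the protocol supports that assumption. Nor do the documents support extending the loss to nonserious irAEs after new therapy, because these are never recorded.

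The conclusion rests on the earlier-of reading and on the SAP not overriding the default. It is a minor-to-moderate improvement to secondary descriptive summaries.

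**What to change.** In section 9.4.3.2, and in the SAP for each sub-study:

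1. Keep the on-treatment summary, but state its end as the earlier of 30 days after last dose of study treatment and the day before the first new anti-cancer drug.
2. Add a summary of SAEs and AESIs from first dose to 90 days after last dose of study treatment.
3. In that summary, count SAEs (including serious irAEs) irrespective of new anticancer therapy and flag those with onset after it. End nonserious AESIs at the start of new therapy, because recording stops there.

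No new data are needed. The cost is a definition and one extra table. The downside is that rates will be somewhat higher and some events will be confounded by subsequent therapy, which the flag makes visible.

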##### 9.4.3.2.1. Adverse Events

AEs will be graded by the investigator according to the CTCAE version 5.0 and coded using the MedDRA. AE data will be reported in tables and listings. Summaries of AEs by mapped terms, appropriate thesaurus level, toxicity grade, and seriousness and relationship to study treatment will be presented, as well as summaries of AEs leading to death and premature

withdrawal from study treatment. The number and percentage of participants who experienced any AE, SAE, treatment related AE, and treatment related SAE will be summarized. Listings of DLTs and deaths will be provided.

#### **9.4.3.2.2. Laboratory Test Abnormalities**

The number and percentage of participants who experienced laboratory test abnormalities will be summarized according to worst toxicity grade observed for each laboratory assay using shift tables. For laboratory tests without CTCAE grade definitions, results will be categorized as normal, abnormal, or not done.

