### 2.2.2. Clinical Overview

Sasanlimab is being evaluated as a single-agent in Study B8011001 (146 participants with locally advanced or metastatic melanoma, squamous cell carcinoma of the head and neck, ovarian cancer, sarcoma, NSCLC, UC, or other solid tumors); as a single-agent in Study B8011007 (8 participants with advanced malignancies); and in combination with BCG in Study B8011006 (20 participants with high risk non muscle invasive bladder cancer).

Anti-tumor activity of single-agent sasanlimab has been demonstrated in Study B8011001. As of the data cutoff of 01 November 2019, efficacy has been evaluated in 67 participants with NSCLC and 38 participants with UC who were administered sasanlimab 300 mg SC Q4W. The ORR (95% Exact CI) was 20.9% (11.9%-32.6%) in the NSCLC cohort and 21.1% (9.6%-37.3%) in the UC cohort. Median (range) duration of partial response was 230 days (57-445 days) in the NSCLC cohort and 183 days (23-371 days) in the UC cohort.

A total of 60 of 106 participants who were administered sasanlimab 300 mg SC experienced at least 1 treatment-related AE. Most commonly (>5%) reported treatment-related AEs were hyperthyroidism (10.4%), pruritus (7.5%), lipase increased (6.6%), and ALT increased, AST increased, amylase increased, hypothyroidism, rash, and anemia (5.7% each).

Sixteen (15.1%) participants reported  $\geq$  Grade 3 treatment related AEs. Grade 3 treatment-related AEs included lipase increased, amylase increased, and blood alkaline phosphatase increased (1.9% each); decreased appetite, hypermagnesemia, pneumonitis, ageusia, anosmia, jaundice, blood potassium increased, transaminases increased, lymphocyte count decreased, asthenia, fatigue, cognitive disorder, and hypotension (0.9% each). Grade 4 treatment-related AEs included lipase increased, neutrophil count decreased, and white blood cell count decreased (0.9% each). Grade 5 treatment-related AE included arrhythmia (n = 1, 0.9%).

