Injection site reactions were infrequent, occurring in <5% of patients. Because monoclonal antibodies may cause reactions such as pain or erythema at the injection site, local tolerability to sasanlimab injections will be assessed. The irAE profile of sasanlimab is mostly consistent with the known safety profile of anti-PD-1 treatment. Treatment-related irAEs commonly identified for sasanlimab include hypothyroidism, hyperthyroidism, and pneumonitis; these have been categorized as ADRs for sasanlimab.

Detailed safety information from clinical studies, as well as nonclinical information, can be found in the sasanlimab (PF-06801591) IB.

Please see [Section 12.2.2.1](#) for a discussion of the clinical overview of investigational products used in combination with sasanlimab in Sub-study A, and [Section 13.2.2.3](#) for agents used in Sub-Study B.

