### Medical Conditions:

1. Active or prior autoimmune disease that might deteriorate when receiving an immunostimulatory agent. Participants with diabetes type I, vitiligo, psoriasis, or hypothyroid or hyperthyroid disease not requiring immunosuppressive treatment are eligible.
2. Previous Grade  $\geq 3$  irAE; or unresolved irAEs prior to first dose of study intervention.
3. Active non-infectious pneumonitis, pulmonary fibrosis, or known history of immune-mediated pneumonitis.
4. Active infection requiring systemic therapy.

5. Clinically significant cardiovascular diseases, including any of the following:
  - a) History of acute myocardial infarction, acute coronary syndromes (including unstable angina, coronary artery bypass graft, coronary angioplasty or stenting)  $\leq 6$  months prior to start of study treatment;
  - b) Congestive heart failure requiring treatment (New York Heart Association Class  $\geq 2$ );
  - c) Uncontrolled hypertension defined as persistent systolic blood pressure  $\geq 150$  mmHg or diastolic blood pressure  $\geq 100$  mmHg despite optimal therapy;
  - d) History or presence of clinically significant or uncontrolled sustained cardiac arrhythmias (including uncontrolled atrial fibrillation or uncontrolled paroxysmal supraventricular tachycardia);
  - e) History of thromboembolic or cerebrovascular events  $\leq 3$  months prior to the first dose of study treatment. Examples include transient ischemic attacks, cerebrovascular accidents, hemodynamically significant (ie, massive or sub-massive) deep vein thrombosis or pulmonary emboli.  
*Note:* Participants with either deep vein thrombosis or pulmonary emboli that do not result in hemodynamic instability are allowed to enroll as long as they are stable, asymptomatic and on stable anticoagulants for at least 2 weeks.  
*Note:* Participants with thromboembolic events related to indwelling catheters or other procedures may be enrolled.
6. Other malignancy within 2 years prior to the first dose of study intervention, except for adequately treated basal cell or squamous cell skin cancer, or carcinoma in situ of the breast or of the cervix, or low-grade (Gleason 6 or below) prostate cancer on surveillance without any plans for treatment intervention (eg, surgery, radiation, or castration) or other concurrent malignancy investigator feels has a very low likelihood to become metastatic.

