Hypopituitarism/ Hypophysitis (secondary endocrinopathies)	
 
-If secondary thyroid and/or adrenal insufficiency is confirmed (ie, subnormal serum FT4 with inappropriately low TSH and/or low serum cortisol with inappropriately low ACTH):               
 
-Refer to endocrinologist for dynamic testing as indicated and measurement of other hormones (FSH, LH, GH/IGF-1, PRL, testosterone in men, estrogens in women)
 
-Hormone replacement/suppressive therapy as appropriate
 
-Perform pituitary MRI and visual field examination as indicated
 
 
 
-If hypophysitis is confirmed: 
 
-Continue study treatment if mild symptoms with normal MRI. Repeat the MRI in 1 month
 
 
 
	
 
-Resume study treatment once symptoms and hormone tests improve to Grade <math>\leq</math> 1 (with or without hormone replacement).
 
-In addition, for hypophysitis with abnormal MRI, resume study treatment only once shrinkage of the pituitary gland on MRI/CT scan is documented.
 
-Continue hormone replacement/suppression therapy as appropriate.
 

Endocrine irAEs		
Endocrine Disorder	Initial Management	Follow-up Management
	
-Withhold study treatment if moderate, severe or life-threatening symptoms of hypophysitis and/or abnormal MRI. Consider hospitalization. Initiate corticosteroids (1 to 2 mg/kg/day prednisone or equivalent) followed by corticosteroids taper during at least 1 month
 
-Add prophylactic antibiotics for opportunistic infections
	

Other irAEs* (not described above)		
Grade of other irAEs (NCI-CTCAE v5.0)	Initial Management	Follow-up Management
Grade 2 or Grade 3 clinical signs or symptoms suggestive of a potential irAE	-Withhold study treatment pending clinical investigation	-If irAE is ruled out, manage as appropriate according to the diagnosis and consider re-starting study treatment -If irAE is confirmed, treat as Grade 2 or 3 irAE.
Grade 2 irAE or first occurrence of Grade 3 irAE	-Withhold study treatment -1.0 to 2.0 mg/kg/day prednisone or equivalent -Add prophylactic antibiotics for opportunistic infections -Specialty consult as appropriate	-If improves to Grade $\leq$ 1: -Taper steroids over at least 1 month and resume study treatment following steroids taper.

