**Table 5. Schedule of Activities Sub-Study A Phase 1b and Phase 2**

Visit Identifier a Abbreviations used in this table may be found in Appendix 11, Section 10.11	Screening b (≤28 days prior to first dose)	Treatment Period										Follow-Up e		
		Cycle 1 c (Days 1 to 28)			Cycle 2 c (Days 1 to 28)		Cycle 3 & 4 (Days 1 to 28)	Cycle 5 (Days 1 to 28)		Cycle ≥6 (Days 1 to 28)				
		Day 1	Day 8 (Phase 1b Only)	Day 15	Day 1	Day 15	Day 1	Day 1	Day 8 (Phase 1b Only)	Day 1	EOT d	Day 30 e	Day 60, Day 90, Day 180 e	Survival e
										8 weeks thereafter				
Laboratory Assessments of Hematology and Blood Chemistry n	X	X	X	X	X	X	X	X	X	X	X	X		
Coagulation n	X	X		X		X	X		X	X	X			
Urinalysis o	X	X								X	X			
Pregnancy test p	X	X		X		X	X		X	X	X	X		
Hepatitis B, C tests q	X													
Endocrinology tests n	X					Every 4 cycles starting at C4D1								
Allocation to study intervention r		X												
Administration of study treatment (sasanlimab) s		X			X		X	X		X				
Administration of study treatment (encorafenib) t		Continuous QD												
Administration of Study treatment (binimetinib) u		Continuous BID												
Dispensing of encorafenib and binimetinib		X			X		X	X		X				
Local site injection tolerability assessment v		X			X		X	X		X				
Tumor assessment w	X	Every 8 wks (±7 days) from C1D1 for the first 18 months, then every 12 wks (±7 days) thereafter according to calendar, regardless of treatment delays and until progressive disease assessed by investigator using RECIST v1.1 or start of new anti-cancer therapy												
Patient Reported Outcomes: EORTC QLQ-C30/LC13 x		X			X		X	X		X	X			

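### Laboratory tests without CTCAE grades are classed only as normal or abnormal, so the laboratory summary loses the direction of change for any such test that can go low or high

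*Protocol*

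**What the plan says.** Section 9.4.3.2.2 sets two rules for laboratory abnormalities. Graded tests are to be "summarized according to worst toxicity grade observed for each laboratory assay using shift tables". For the rest: "For laboratory tests without CTCAE grade definitions, results will be categorized as normal, abnormal, or not done". Neither rule mentions low versus high, and shift tables are named only in the rule for graded tests.

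The summaries serve a named endpoint. Change in laboratory parameters is part of the secondary safety endpoint in Phase 1b and Phase 2 of both sub-studies (Tables 6 and 24). The required panel in section 10.2, Table 4, includes ACTH, TSH and free T4. In Sub-Study A these are taken at screening and then "Every 4 cycles starting at C4D1" (Table 5); Table 23 gives Sub-Study B the same timing.

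On the drug itself, section 2.2.2 says: "Treatment-related irAEs commonly identified for sasanlimab include hypothyroidism, hyperthyroidism, and pneumonitis".

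**The concern.** A result outside the reference range can lie on either side of it, and for some tests the side is the finding. Thyroid function is the natural example, because the backbone antibody can move it either way. The protocol's own endocrine guidance in section 10.10 turns on direction when it describes secondary disease as "subnormal serum FT4 with inappropriately low TSH". Exclusion criterion 1 in section 5.2 also lets in people with existing thyroid disease: those with "hypothyroid or hyperthyroid disease not requiring immunosuppressive treatment are eligible". Some participants may therefore start outside the range and cross to the other side.

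At stake is whether the laboratory half of the secondary safety endpoint can describe change at all for such tests. A table that says only that a value was abnormal does not say how it changed.

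**Working it through.** The plan attaches no figure to this rule, so there is nothing to reproduce. The check is what the stated classes keep, and what other planned summaries recover.

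**1. What the classes keep.** Take an ungraded test that can be abnormal both ways, and set baseline against one on-treatment result.

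- With low, within and high there are 3 × 3 = 9 possible cells.
- With normal and abnormal there are 2 × 2 = 4.
- Normal to normal holds 1 of the 9 cells.
- Normal to abnormal merges 2: within to low, and within to high.
- Abnormal to normal merges 2: low to within, and high to within.
- Abnormal to abnormal merges 4: low to low, low to high, high to low, high to high.
- Check: 1 + 2 + 2 + 4 = 9.

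The direction of new abnormalities is lost, and a full reversal cannot be told from no change. The split cannot be recovered from the table.

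**2. Which tests this touches.** The protocol does not list the tests that lack CTCAE grades. TSH, free T4 and ACTH may be among them, but that is an assumption. The argument in step 1 applies to any ungraded test that can be abnormal in both directions, whichever those are.

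**3. What other summaries recover.** Section 9.4.3.2.1 summarises adverse events by mapped term and grade. Section 8.3.8 makes any adverse event suspected to be immune-related an event of special interest, and section 9.4.3.2 summarises those. Hypothyroidism and hyperthyroidism recorded as adverse events therefore appear apart.

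**4. What is not recovered.** Under section 10.3.1 a laboratory abnormality becomes an adverse event if the investigator judges it clinically significant, or if it comes with symptoms, leads to further testing or intervention, or changes dosing or treatment. An out-of-range result that meets none of these need not be recorded as an event. Special-interest status requires an adverse event first, so it passes through the same filter. For these results the laboratory table is the only planned summary, and it has no direction.

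**5. Graded tests.** The text gives one worst grade per assay. It does not say that low-direction and high-direction grades are pooled, nor that they are kept apart. Sodium, potassium and magnesium are single lines in Table 4, while the protocol elsewhere reports directional toxicities such as hypermagnesemia, raised potassium (section 2.2.2) and hyponatremia (section 12.2.2.1). The wording is open here rather than wrong.

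**The case against.** The strongest reply is that the adverse event tables already do the job. They separate hypo- from hyperthyroidism by term, and results that matter clinically must be recorded as events. This stands for recorded events. A reader might infer from the laboratory rule that opposite thyroid effects cannot be distinguished anywhere in the report, and the documents do not support that. The reply does not cover results left unrecorded as events. The endpoint also names laboratory change as a component of its own, beside adverse events.

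Second, section 9 says the SAP gives detail and may modify the outline, and section 9.4.3.2 leaves room for the SAP to specify otherwise. That is true, and the SAP may already split direction. But the protocol does not leave the classification open: it chooses one. A SAP that follows it as written inherits the loss.

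Third, a reader might project the sasanlimab rates in section 2.2.2 (10.4% hyperthyroidism, 5.7% hypothyroidism) onto the planned enrolment and count the merged cases. Those are rates of treatment-related adverse events, exactly the cases that the event tables keep apart, so they do not measure what the laboratory table loses. Pooling the sub-studies for such a count would also go against section 9.4.1, which reports each sub-study and phase separately.

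Fourth, a reader might take the graded-test rule as merging high and low electrolytes. That is inference. The protocol's own graded laboratory terms are directional, and this part supports only a request for clarity.

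Finally, the endocrine guidance in section 10.10 is applied to an individual's actual results, not to a summary table. It shows that direction carries meaning, not that anyone's management would suffer.

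**Conclusion.** The point holds in a narrow form. For laboratory tests without CTCAE grades, the stated classes merge low and high, so the laboratory summary cannot show direction for any such test that can be abnormal both ways, and it hides reversals. The loss is confined to that table and to changes not recorded as adverse events.

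Its size cannot be put in numbers from the documents. They give neither the list of ungraded tests nor a rate of out-of-range results that go unrecorded as events. The thyroid and ACTH examples rest on the assumption that these tests are ungraded; the general point does not.

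Severity is minor. This is the layout of a descriptive summary for a secondary safety endpoint. No hypothesis test, sample size, dose decision or individual safety monitoring depends on it, and results stored with their reference ranges can be re-tabulated.

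**What to change.** In section 9.4.3.2.2, replace the classes for ungraded tests with below, within or above the reference range, or not done. Show shifts from the baseline class to the lowest and to the highest on-treatment class, so that a participant who goes both ways is seen in both.

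Add one clarifying sentence for graded assays that can be abnormal in both directions: low and high grades are tabulated separately.

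The cost is table programming and a few more tables. Section 10.2 already requires laboratories to supply reference range documents for each test used, so no new sampling is needed, provided the results themselves and not only a normal/abnormal flag are in the database.
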